9.0 EVALUATION CRITERIA

The present study is designed to evaluate the effect of β -adrenergic blockade and R/GI on advanced incurable cervical cancer.

We define this trial to be feasible if FACT Cx, BPI, HADS, and MDASI scores can be calculated for (1) all evaluable subjects at baseline, (2) 87% of subjects (13 out of 15) at Month 2, and (3) 73% of subjects (11 out of 15) at Month 4. Patients are considered nonevaluable if they leave the study through disease specific death or progressive disease prior to Month 4, and they will be replaced. Disease specific death does not include death due to excessive toxicity. All other patients are considered evaluable.

10.0 DURATION OF STUDY

Feasibility is determined by completion of three time points (TP0, 2, 4 mos). Patients who wish to continue on the regimen may do so until voluntary discontinuation, intolerability, disease progression, or death. The patient will be followed until death with assessment of medical notes in clinic station.

We will terminate the study early if too many patients experience dose-limiting toxicities (DLTs).

If removed from study, all patients will be weaned off the medication over the following 2 weeks. The dose will be reduced by 50% for 7 days then will be reduced to 25% of the dose for 7 days then discontinue completely. For patients that experience adverse effects during weaning the period of time can be increased as deemed appropriate.

11.0 STUDY MONITORING AND REPORTING PROCEDURES

A consent form must be signed by the patient prior to entry into study. Current Federal Drug Administration (FDA), National Cancer Institute (NCI) and institutional regulations concerning informed consent will be followed.

11.1 Reporting an Adverse Event.

11.1.1 An Adverse Event (AE) is any unfavorable and unintended sign (including abnormal lab finding), symptom, or disease that occurs in a patient administered a medical treatment, whether the event is considered related or unrelated to the medical treatment.

11.1.2 In the event of a serious adverse event (SAE) the first concern will be for the safety of the subject. Investigators are required to report to the Principal Investigator, who in turn must notify the IRB of any serious adverse events (SAE'S) that are possibly related to the study therapy, as per MDACC IRB guidelines.

11.1.3 An SAE is any sign, symptom or medical condition that emerges with propranolol treatment or during a post-treatment follow-up period that:

- (1) was not present at the start of treatment and is not a chronic condition that is part of the patient's medical history, OR
- (2) was present at the start of treatment or as part of the patient's medical history but worsened in severity and/or frequency during therapy.

AND that meets any of the following regulatory serious criteria:

- Results in death
- Is life-threatening
- Requires or prolongs inpatient hospitalization
- Is disabling
- Is a congenital anomaly/birth defect
- Is medically significant or requires medical or surgical intervention to prevent one of the outcomes listed above.

11.1.4 This study will utilize the Common Toxicity Criteria version 4.0 (CTC 4.0) for defining and grading specific adverse events.

Specific situations that require reporting to the IRB are summarized in the table below.

		Unrelated Unlikely	Possible Probable Definite
Grade 1	Unexpected & Expected	Not Required	Not Required
Grade 2	Unexpected	Not Required	7 Calendar days
	Expected	Not Required	Not Required
Grade 3	Unexpected with hospitalization	7 Calendar days	7 Calendar days

	Unexpected without hospitalization	Not Required	7 Calendar days
Grade 3	Expected with hospitalization	7 Calendar days	7 Calendar days
	Expected without hospitalization	Not Required	Not Required
Grade 4 & 5	Unexpected	24 hours	24 hours 3 Calendar days
Grade 4 & 5	Expected	24 hours	24 hours 7 Calendar days

- 1) “24 hours; 3 calendar days” - the investigator must initially report the AE within 24 hours of learning of the event followed by a complete report within 3 calendar days of the initial 24 hour report.
- 2) “7 calendar days” - a complete report on the AE must be submitted to the IRB within 7 calendar days of the investigator learning of the event.

11.1.5 Any medical event equivalent to a CTCAE grade 3, 4 or 5 that precipitates hospitalization must be reported regardless of attribution and designation as expected or unexpected with exception of any events identified as protocol-specific expedited adverse event reporting exclusions. This includes any grade 4 laboratory abnormalities that result in hospitalization.

11.1.6 Any event that results in persistent or significant disabilities/incapacities, congenital anomalies, or birth defects must be reported if the event occurs.

11.2 Assessing Causality:

Investigators are required to assess whether there is a reasonable possibility that propranolol, caused or contributed to an adverse event. The following general guidance may be used

11.2.1 *Yes*: if the temporal relationship of the clinical event to propranolol, administration makes a causal relationship possible, and other drugs, therapeutic interventions or underlying conditions do not provide a sufficient explanation for the observed event.

11.2.2 *No*: if the temporal relationship of the clinical event to propranolol, administration makes a causal relationship unlikely, or other drugs, therapeutic interventions or underlying conditions provide a sufficient explanation for the observed event.

11.3 Severe Adverse Event reporting:

11.3.1 The following events will require a **serious adverse event** report to be completed and reported to the Principal Investigator and the MD Anderson Cancer Center Institutional Review Board.

- Unanticipated side effect (not mentioned in consent, protocol or drug brochure)
- Event exceeds the nature, severity or frequency described in consent, protocol or drug brochure.
- Event involves a discrepancy between what was actually done to the research subject and what the subject was informed of when signing consent.
- Event requires discontinuation of study drug use.
- Event necessitates admission to hospital unless the hospitalization is anticipated due to the subject's disease or treatment.
- Event prolongs a stay in a health care facility.
- Event necessitates supportive treatment to prevent permanent impairment or damage.
- Event negatively affects prognosis.
- Event results in a new cancer.
- Event results in significant, persistent or permanent harm or disability*.
- Event results in death.
- Any death within 30 days of receiving study drug.
- A congenital anomaly/birth defect.
- Event necessitates supportive treatment to prevent permanent impairment or damage.

* Definition of disability: A substantial disruption of a person's ability to conduct normal life functions.

11.3.2 Important medical events that may not result in death, be life-threatening, or require hospitalization may be considered a serious adverse drug experience when, based upon appropriate medical judgment, they may jeopardize the patient or subject and may require medical or surgical intervention to prevent one of the outcomes listed in this definition.

- **Life-threatening adverse drug experience:** Any adverse drug experience, including grade 4 laboratory abnormalities, that places the patient or subject, in the view of the investigator, at immediate risk of death from the reaction as it occurred, i.e., it does not include a reaction that, had it occurred in a more severe form, might have caused death.
- **Unexpected adverse drug experience:** Any adverse drug experience, the specificity or severity of which is not consistent

with the current Investigator Brochure; or if an Investigator Brochure is not required or available, the specificity or severity of which is not consistent with the risk information described in the general investigational plan or elsewhere in the current application, as amended.

- **“Unexpected”**, as used in this definition, refers to an adverse drug experience that has not been previously observed (i.e., is not included in the Investigator Brochure) rather than an experience that is not anticipated based on the pharmacological properties of the pharmaceutical product.

12.0 STATISTICAL CONSIDERATIONS:

This is a feasibility study. Feasibility is defined in terms of patient enrollment, completion of survey scales, and safety of beta-blocker regimen. Specifically, we will consider this trial feasible if:

1. on average, we enroll at least 1-2 patients each month.
2. FACT-Cx, BPI, HADS, and MDASI scores can be calculated for (1) all evaluable subjects at baseline, (2) 87% of subjects (13 out of 15) at Month 2, and (3) 73% of subjects (11 out of 15) at Month 4; and
3. $\Pr(\pi_t \leq 0.2 \mid \text{data}) > 90\%$ where π_t is the proportion of any grade 3-4 toxicities that are probably, possibly, or definitely related to the intervention.

Scores for the FACT-Cx can be calculated when at least 50% of the items on each subscale have been answered. A total score for the FACT-Cx can be calculated when at least 80% of the total items have been answered and each subscale has a score.

Scores for BPI: Pain Severity can only be calculated when all 4 items have been answered. Scores for BPI: Pain Interference can be calculated when at least 4 out of the 7 items have been completed.

Scores for HADS: Anxiety can be calculated when at least 6 of the 7 anxiety items have been completed. Likewise, scores for HADS: Depression can be calculated when at least 6 of the 7 depression items have been answered.

Scores for MDASI: Symptom Severity can be calculated when at least 7 of the 13 items have been completed. Scores for MDASI: Symptom Interference can be calculated when at least 4 of the 6 items have been completed.

Patients are considered nonevaluable if they leave the study through disease-specific death or progressive disease prior to Month 4, and they will not be replaced. Disease-specific death does not include death due to excessive toxicity. All other patients are considered evaluable. In addition to calculating the percent of women who complete these quality of

life (QoL) measures, we will calculate the percent of women completing combined intervention of twice daily beta blocker and twice weekly progressive muscle relaxation and guided imagery at Month 2 and Month 4.

The secondary objectives of this study are to estimate the impact of beta blocker and relaxation intervention on symptoms, anxiety, depression, pain and QoL. We will examine symptoms and symptom distress using the MDASI, anxiety and depression using HADS, pain using the BPI and QoL using the Trial Outcome Index (TOI) of the FACT-Cx.

The exploratory objectives of this study are to measure changes in serum levels of IL-6, IL-8, IL-10, VEGF, CRP, and resting energy use via calorimeter, as well as to measure HPV components (e.g. E6 and E7) in circulating cell-free DNA.

All secondary and exploratory endpoints will be examined graphically and through summary statistics. Ninety percent confidence intervals will be calculated for all endpoints, including feasibility endpoints.

We will recruit 20 patients to obtain 15 evaluable patients. With 15 subjects, if we have data for 87% of the women at Month 2 and 73% of the women at Month 4, our exact 90% confidence intervals at Months 2 and Months 4 will extend from 64% to 98% at Month 2 and 49% - 90% at Month 4. Additionally, with 15 subjects, the boundaries of our 90% confidence interval for sample means will extend 0.43 standard deviations on either side of the sample mean. We will also track number of patients approached and, if appropriate, reasons for declining to participate.

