6.0 SAFETY PLAN AND CRITERIA FOR REMOVAL FROM STUDY

6.1 Patient Safety

A number of measures will be taken to ensure the safety of patients participating in this trial. These measures will be addressed through exclusion criteria (see Section 3.2) and routine monitoring as follows:

Patients enrolled in this study will be evaluated clinically and with standard laboratory tests before and at regular intervals during their participation in this study. Safety evaluations will consist of medical interviews, recording of adverse events, physical examinations, blood pressure, and laboratory measurements (see Section 8.1). Patients will be evaluated for adverse events (all grades), serious adverse events, and adverse events requiring study drug interruption or discontinuation at each study visit for the duration of their participation in the study. Patients discontinued from the treatment phase of the study for any reason will be evaluated approximately 30 days (28-42 days) after the decision to discontinue treatment.

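### The only quantified safety criterion counts grade 3-4 toxicities and leaves out related deaths (grade 5); its unit of counting is also unclear

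*Combined protocol and SAP*

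**What the plan says.** Section 12.0 makes the trial feasible if three conditions hold: enrolment, survey completion, and a toxicity condition. The third requires Pr(π_t ≤ 0.2 | data) > 90%, where π_t "is the proportion of any grade 3-4 toxicities that are probably, possibly, or definitely related to the intervention". It gives no prior, no analysis population and no pass count.

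The second condition requires scores for all evaluable patients at baseline, for "87% of subjects (13 out of 15) at Month 2, and (3) 73% of subjects (11 out of 15) at Month 4". On who is evaluable, Section 12.0 says "Disease-specific death does not include death due to excessive toxicity" and then "All other patients are considered evaluable". A patient who dies of toxicity therefore stays in the denominator of criterion 2.

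Section 11 uses grade 5 throughout. The IRB reporting table in 11.1.4 has a combined row for grades 4 and 5 and a column for attribution headed "Possible Probable Definite". Section 11.1.5 says "Any medical event equivalent to a CTCAE grade 3, 4 or 5 that precipitates hospitalization must be reported". Section 10.0 says the study will end early if too many patients have dose-limiting toxicities, but gives neither a number nor a definition of such a toxicity.

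**The concern.** Grade 5 is the worst outcome on the scale that the plan adopts, and the plan expects that it might occur. Yet a related death adds nothing to π_t, and no other section adds it. Fatal toxicity reaches the feasibility verdict only through criterion 2, which measures survey completion and treats every missing survey alike. The trial could then be called feasible, safety included, after several related deaths.

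A secondary point is the unit. Read literally, the sentence describes a share of toxicities. A share of patients was probably meant, since Section 10.0 speaks of patients, but the text does not say so and does not say which patients count. On the literal reading, a larger number of unrelated toxicities would make the regimen look safer.

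**Working it through.** **Inputs from the plan.** Threshold 0.2 and certainty 90% (Section 12.0, criterion 3); 13/15 and 11/15 (criterion 2); 20 recruited to obtain 15 evaluable (end of Section 12.0).

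**Assumptions.** The prior is not stated, so six are used: Beta(1,1), (0.5,0.5), (0.2,0.8), (0.4,1.6), (1,4), (2,8). Patients are the unit. Fatal events are recorded at grade 5 only. All surviving evaluable patients complete the surveys, and the enrolment condition is met.

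**Reproducing the plan's figures.** Exact (Clopper-Pearson) 90% intervals are 63.7% to 97.6% for 13/15 and 48.9% to 90.3% for 11/15. These match the stated 64% to 98% and 49% to 90%. The plan gives no operating figure for criterion 3 itself.

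**What criterion 2 tolerates.** With 15 evaluable: 15 − 13 = 2 missing at Month 2 and 15 − 11 = 4 missing at Month 4. If all 20 were evaluable: 2 at Month 2 (18/20 = 90%; 17/20 = 85% falls short of 87%) and 5 at Month 4 (15/20 = 75%).

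**Criterion 3.** With x affected of n, the posterior is Beta(a + x, b + n − x). The criterion is met if its distribution function at 0.2 exceeds 0.90.

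| x/n | (1,1) | (0.5,0.5) | (0.2,0.8) | (0.4,1.6) | (1,4) | (2,8) |
|---|---|---|---|---|---|---|
| 0/15 | 0.972 | 0.991 | 0.998 | 0.995 | 0.986 | 0.967 |
| 1/15 | 0.859 | 0.913 | 0.948 | 0.940 | 0.917 | 0.886 |
| 2/15 | 0.648 | 0.726 | 0.793 | 0.785 | 0.763 | 0.736 |
| 4/15 | 0.202 | 0.247 | 0.308 | 0.313 | 0.327 | 0.344 |
| 0/20 | 0.991 | 0.997 | 0.999 | 0.999 | 0.995 | 0.987 |
| 1/20 | 0.942 | 0.968 | 0.982 | 0.978 | 0.967 | 0.948 |
| 2/20 | 0.821 | 0.873 | 0.910 | 0.904 | 0.886 | 0.860 |
| 3/20 | 0.630 | 0.697 | 0.757 | 0.751 | 0.736 | 0.716 |
| 4/20 | 0.414 | 0.477 | 0.544 | 0.543 | 0.540 | 0.537 |

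**Scenarios.**

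- 15 patients, 2 related deaths at any time. Criterion 2 is met even if both fall before Month 2 (13/15). As written, 0/15 passes under all six priors; with deaths counted, 2/15 fails under all six.
- 15 patients, 4 related deaths by Month 4, at most 2 of them before Month 2. Criterion 2 is met (11/15 at Month 4). As written, 0/15 passes; counted, 4/15 fails.
- 20 treated, 15 evaluable, the same 4 deaths. Criterion 2 is met. As written, 0/20 passes; counted, 4/20 fails.
- 20 treated, 1 patient with a related grade 3-4 event plus 2 related deaths. As written, 1/20 passes under all six; counted, 3/20 fails under all six.

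**Limits.** Three deaths before Month 2 fail criterion 2 anyway (12/15, or 17/20), and so do five by Month 4 with 15 evaluable (10/15 = 67%). One death counted at 1/20 still passes under all six priors. Two counted at 2/20 fail under four of six.

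**Unit, with hypothetical counts.** If toxicities were the denominator, 2 related of 10 gives 0.383 to 0.561 (fail) and 2 related of 25 gives 0.916 to 0.963 (pass). The same two related events give opposite verdicts, according to how many unrelated ones occur.

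**The case against.** The strongest reply is that these scenarios are remote. The plan describes propranolol as a drug with few and mostly mild side effects. If the true related-death rate were 1% to 2% per patient (an assumption), the binomial probability of three or more deaths among 20 would be 0.1% to 0.7%, and of two or more among 15, 1.0% to 3.5%. Related grade 4 and 5 events go to the IRB within 24 hours, and Section 10.0 allows early termination, so a trial with several toxic deaths might never reach a feasibility verdict. A patient who dies may also have had an earlier related grade 3-4 event on record, and would then already count.

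Part of this stands. The scenarios are unlikely, and the gap closes for any patient with such an earlier event. But the plan does not require that earlier record. Reporting to the IRB does not put a death into π_t. The Section 10.0 sentence has no number and no definition to apply. A safety criterion is there for unlikely and serious outcomes, and it should not depend on someone deciding afterwards to count what the rule leaves out.

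It is also fair to say that the missing prior and pass count are separate omissions, and that the unit is a wording gap of less weight.

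**Conclusion.** The concern holds. As written, criterion 3 excludes related deaths, and the full feasibility rule can be met with two of them among 15 patients, or with up to four by Month 4 if no more than two fall before Month 2. Counting them would reverse criterion 3 under all six assumed priors. At 20 treated, two deaths alone reverse it under four of the six; two deaths plus one patient with a related grade 3-4 event reverse it under all six. A single death does not change the verdict at 17 to 20 treated; at 15 it does so under two of the six priors. These results rest on the per-patient reading, grade-5-only recording of fatal events, complete surveys from survivors, and priors that the plan does not give. The exclusion of grade 5 itself rests on none of them, because it is in the text. The unit of counting is a secondary and less certain point. This should be fixed.

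**What to change.** In Section 12.0, define π_t as the proportion of treated patients with at least one grade 3-5 event possibly, probably or definitely related to the intervention. State the analysis population, the prior and the resulting pass count in the same place; these are the sponsor's choice. As an illustration, Beta(1,1) on all treated patients allows 0 affected for n = 10 to 16 and 1 for n = 17 to 23. Across the six priors the limit is 0 or 1 at n = 15, 1 at n = 17 to 19, and 1 or 2 at n = 20. With 20 treated and a limit of 1, the binomial probability of meeting the criterion is 74% at a true rate of 5%, 39% at 10% and 6.9% at 20%. No stopping rule is proposed.

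The cost is small. No new data are needed: Section 6.1 already provides that "Patients will be evaluated for adverse events (all grades), serious adverse events" at each study visit. Attribution needs one clarifying line. Section 11.2 says "Investigators are required to assess whether there is a reasonable possibility that propranolol, caused or contributed to an adverse event" and offers only a yes or no answer for propranolol, so the plan should say that the graded scale of the 11.1.4 table feeds criterion 3. The current wording already needs that. The criterion becomes slightly harder to meet.

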1.0 OBJECTIVES

1.1 Primary Objectives:

- 1.1.1 To determine the proportion of patients completing symptom inventory, anxiety and depression survey, pain inventory, and quality of life surveys (MDASI, HADS, BPI, FACT-Cx).
- 1.1.2 To determine the proportion of patients completing combined intervention of twice daily beta blocker use and twice weekly relaxation and guided imagery (R/GI) at two time points (2 mos and 4 mos).

1.2 Secondary Objectives:

- 1.2.1 To index cervix cancer specific symptomatology in this population and the serial change over intervention.
- 1.2.2 To determine the impact of beta blocker and R/GI on symptoms, anxiety and depression, pain, and quality of life (MDASI, HADS, BPI, FACT-Cx)

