R/GI has also been used to address pain in cancer patients. Kwekkeboom et al were able to show improvements in pain intensity, pain-related distress, and perceived control over pain using R/GI but little other data is available in this population [63]. Additional support for this method is detailed in Bonica's Management of Pain [64].

Immunomodulating effects as reported in the Nelson study [50] required extensive interventions such as time consuming phone call commitments and those described in Jon Cabot-Zinn’s mindfulness meditation curriculum, which includes an 8-week review of the benefits and techniques of mindful meditation as well as recommended daily homework [65, 66]. Nelson and colleagues conducted six counseling sessions 45-50 minutes in length (five consecutive weekly sessions and a booster session 1 month after completion of sessions). Most studies suggest that

active/experienced mind-body practice techniques (e.g., mindfulness meditation) can be more effective than less/novice practiced techniques [67, 68].

The literature contains insufficient data to support the exact “dose” in a relaxation stress-reduction intervention [65, 69, 70]. It does contain data supporting good results with experience and increased frequency and duration of practice, but the dose at which such results are obtained remains unknown. According to available data, results require practice most days of the week and sessions at least 20-30 minutes long [20, 67, 68, 71-73]. Most studies showing the effectiveness also demonstrate that reminder phone calls and instruction to practice these interventions daily at home are effective [50, 65, 72].

The present study is designed to evaluate the effect of β -adrenergic blockade and R/GI on advanced incurable cervical cancer. The reason for this Phase II feasibility study design is based on the following:

1. The best clinical practice in these patients is to offer a supportive care consultation if available for symptom control regardless of therapy offered
2. There is concern regarding the feasibility and acceptability for patients nearing the end of their life to accrue to a trial that doesn't use a new agent as its targeted intervention, this design will allow assessment of feasibility/acceptability.

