Feasibility is determined by completion of three time points (TP0, 2, 4 mos). Patients who wish to continue on the regimen may do so until voluntary discontinuation, intolerability, disease progression, or death. The patient will be followed until death with assessment of medical notes in clinic station. Reason for study termination will be recorded.

CT of chest, abdomen, and pelvis will be obtained at baseline within 6 weeks prior to starting treatment and then per MD discretion or worsening of symptoms.

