6.2 Criteria for Removal from Study

- 6.2.1 Patients will be removed from the study if they are unable to tolerate the lowest doses of the regimen because of toxicity.
- 6.2.2 Patients may withdraw from the study at any time for any reason.

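### The only planned survey-completion denominator leaves out patients lost to disease death or progression before Month 4, so the Month 4 rate can only equal or exceed the all-enrolled rate

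*Combined protocol and SAP*

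**What the plan says.** Objective 1.1.1 reads "To determine the proportion of patients completing symptom inventory, anxiety and depression survey, pain inventory, and quality of life surveys". It places no restriction on which patients count.

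Sections 9.0 and 12.0 turn this into a criterion. Scores must be calculable for all evaluable subjects at baseline, for 13 of 15 at Month 2, and for "73% of subjects (11 out of 15) at Month 4". Section 12.0 defines the denominator: "Patients are considered nonevaluable if they leave the study through disease-specific death or progressive disease prior to Month 4". It adds: "Disease-specific death does not include death due to excessive toxicity. All other patients are considered evaluable". Section 9.0 has the same definition. The two sections disagree on replacement: Section 9.0 says nonevaluable patients are replaced and Section 12.0 says they are not.

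On numbers, Section 12.0 says "We will recruit 20 patients to obtain 15 evaluable patients" and gives exact 90% intervals of 64-98% at Month 2 and 49-90% at Month 4, both for 15 subjects.

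On progression, Section 6.2 lists two grounds for removal. One is "Patients will be removed from the study if they are unable to tolerate the lowest doses of the regimen because of toxicity"; the other is voluntary withdrawal. Sections 5.3 and 10.0 name progression as one of the events that end optional continuation, but no section gives criteria for it. CT is done at baseline and "then per MD discretion or worsening of symptoms" (Section 5.3). In the Section 8.1 table the Month 2 scan is done only when clinically warranted. Section 5.3 also provides for recording the reason for study termination.

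**The concern.** Membership of the denominator depends on what happens to the patient after enrolment. A patient who progresses but stays and fills in the forms counts as a success. One who progresses and leaves is deleted and never counts as a failure. Eligibility takes incurable, previously treated patients with performance status up to 3, and bars other antineoplastic treatment for the four months, so such exits will not be rare. The plan itself allows for 5 in 20.

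Three consequences follow. The Month 4 figure describes patients who did not leave through disease, while the objective asks about patients. The Month 2 figure depends on events in Months 3 and 4. And because progression is undefined, whether a lost patient is deleted or counted as a non-completer is a judgement made once she is already lost. Section 2.6 says a randomised phase II is to follow. If its expected data completeness were taken from the evaluable rate alone, it would be set too high for the patients actually enrolled.

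**Working it through.** **Inputs.** 20 recruited and 15 evaluable, hence 20 − 15 = 5 nonevaluable (5/20 = 25%, implied by Section 12.0, not stated). Thresholds 13/15 and 11/15 (Sections 9.0 and 12.0). Two-sided exact 90% intervals (Section 12.0).

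**Step 1: reproduce the plan's intervals.** Clopper-Pearson for x of n: the lower limit is the 5% quantile of Beta(x, n − x + 1) and the upper limit is the 95% quantile of Beta(x + 1, n − x).
- 13/15 = 86.7%: 63.7% to 97.6%. The plan gives 64-98%.
- 11/15 = 73.3%: 48.9% to 90.3%. The plan gives 49-90%.

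Both match.

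**Step 2: Month 4.** Let c be the number completing at Month 4, N the number enrolled and e ≤ N the number evaluable. Taking departure before Month 4 to mean departure before the Month 4 survey, nonevaluable patients add nothing to c. The two rates are c/e and c/N, and c/e ≥ c/N always. At the plan's numbers:
- evaluable: 11/15 = 73.3% (48.9-90.3%)
- all enrolled: 11/20 = 55.0% (34.7-74.1%)
- difference: 18.3 percentage points.

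**Step 3: Month 2.** Nonevaluable patients may or may not have completed Month 2 before leaving. With 13 of 15 evaluable completing, let k of the other 5 also have completed. The all-enrolled rate is (13 + k)/20:
- k = 0: 13/20 = 65% (44.2-82.3%)
- k = 5: 18/20 = 90% (71.7-98.2%).

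The evaluable figure of 86.7% lies inside this range. The rule deletes Month 2 completers who later leave as well as non-completers, so the direction of the error is not fixed.

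**Step 4: sensitivity to one label.** Start from 20 enrolled, 5 exits classed as progression or disease death, and 11 completers at Month 4. Class one of the 5 as another reason and she returns to the denominator as a non-completer: 11/16 = 68.75%, below 73%. With 16 evaluable, 12/16 = 75% would be needed.

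**Step 5: dependence on replacement.** The 55% assumes exactly 20 enrolled and 5 nonevaluable. If patients are replaced until 15 are evaluable (Section 9.0) and a share q is nonevaluable, enrolment is 15/(1 − q), and the all-enrolled rate at the Month 4 threshold is 11(1 − q)/15:

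| q | Enrolled | All-enrolled rate |
|---|---|---|
| 10% | 16.7 | 66% |
| 25% | 20 | 55% |
| 40% | 25 | 44% |
| 50% | 30 | 37% |

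If patients are not replaced (Section 12.0) and more than 5 are nonevaluable, fewer than 15 remain and a threshold written out of 15 is undefined.

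**Step 6: illustration only.** Section 2.1 cites median survivals of 9.4 and 6.5 months. Treated as exponential from entry, death by Month 4 is 1 − 0.5^(4/9.4) = 26% or 1 − 0.5^(4/6.5) = 35%, before any exit for progression. With 20 enrolled and no replacement, the binomial chance of at least 15 evaluable is 0.60 or 0.25. Those medians come from a different, chemotherapy-treated population and the exponential shape is assumed, so nothing above rests on them.

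**The case against.** The rule is pre-specified and openly stated, and it answers a legitimate question: among patients whom the disease does not take out of the study, can the surveys be completed? Counting every disease death as survey non-completion mixes mortality with burden and willingness. That stands, and it is why the evaluable rate should be kept. It does not justify making it the only rate, because objective 1.1.1 is not restricted in that way.

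The information on exits is also partly planned already, since the reason for termination is to be recorded. That stands too, and it makes the remedy cheap.

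A reader might infer four stronger things that the documents do not support.
- *That reaching 11/15 makes the trial feasible.* It meets only the Month 4 component. Complete baseline scores, 13/15 at Month 2, the accrual rate and the toxicity criterion are also required.
- *That the rule removes end-of-life patients as a group.* All enrolled patients meet the same eligibility. Only those leaving through disease death or progression before Month 4 are removed; toxic deaths and other withdrawals stay in.
- *That the Month 2 rate is also biased upward.* Step 3 shows it can err in either direction.
- *That Section 2.6 frames the study around whether such patients can complete the programme.* The words "There is concern regarding the feasibility and acceptability for patients nearing the end of their life" continue into accrual to a trial without a new agent. Accrual has its own criterion, which this rule does not touch. The case here rests on objective 1.1.1.

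**Conclusion.** The concern holds for the denominator. At Month 4 the evaluable rate cannot fall below the all-enrolled rate, and at the plan's own 20 and 15 the gap at the threshold is 73% against 55%. That needs no outside figure, only exactly 20 enrolled and 5 nonevaluable; under replacement it widens or narrows with the nonevaluable share. At Month 2 the denominator is wrongly timed, with an all-enrolled rate anywhere from 65% to 90% against 87% and no fixed direction of error. With progression undefined and imaging after baseline discretionary, one reclassified exit is enough to take the Month 4 component from 73% to 69%. Whether 15 evaluable patients will be reached is a separate question that the survival illustration cannot settle. This is something the sponsor should correct; it does not invalidate the study.

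**What to change.** Amend Sections 9.0 and 12.0 as follows.

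(a) Report Month 2 and Month 4 completion for all enrolled patients, with exact 90% intervals, beside the evaluable rates, and tabulate exits by reason. State that the evaluable rate applies only to patients who did not leave through disease death or progression, and state which denominator decides feasibility. If the all-enrolled rate is to decide, the bar needs fresh thought: 73% of 20 is 14.6, so 15/20, and with 5 lost to disease all 15 others would have to complete.

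(b) For the Month 2 rate, treat as nonevaluable only patients who left through disease death or progression before the Month 2 window.

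(c) For the analysis, count an exit as progression only where it was documented (imaging or a dated clinical note) before the missed survey. Otherwise count it as non-completion.

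(d) Reconcile Sections 9.0 and 12.0 on replacement, and express the thresholds as proportions so that they remain defined if the evaluable number is not 15.

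This takes no extra visits, patients or procedures, and uses the reason for termination that is already to be recorded. The price is that the reported Month 4 completion figure becomes less favourable.
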